## Appendix A Schedule of Procedures – Weekly and Every 2 Week Dosing *Continued*

- j Blood samples to be collected after an overnight fast of at least 10 hours and preferably not more than 12 hours, unless tests are repeated for safety reasons.
- k If the platelet value, serum creatinine or liver enzyme tests are uninterpretable (e.g., due to clumping, hemolysis or quantity not sufficient) a repeat blood specimen should be re-drawn as soon as possible (ideally within 7 days). All platelet count results will be reviewed promptly (within 48 hours of receipt) by the Investigator as per [Section 6.2.1](#). Any case of a platelet count  $\leq 50,000/\text{mm}^3$  should be reported in an expedited fashion to the Sponsor.
- l Refer to [Appendix C](#) for PK Sampling schedule.
- m Women who are not surgically sterile or post-menopausal.
- n Serum and plasma samples will be collected and stored for follow-up exploration of laboratory findings and/or AEs (e.g., measurement of cytokine and/or chemokine levels, measurement of additional markers of kidney function, measurement of antibodies, etc.) in this or subsequent clinical studies of ISIS 681257.
- o Patients will continue treatment in the study until the last patient enrolled reaches 6 months of exposure, and 50% of the enrolled patients have received Study Drug for 52 weeks. When both of these milestones are met, all patients will then enter a 16-week post-treatment follow-up period.

### Time (time is in reference to Study Drug administration):

- 1 24-hr from previous dose of Study Drug
- 2 48-hr from previous dose of Study Drug
- 3 Pre-dose, 1, 2, 4, 8 hours post SC injection

**Appendix A Schedule of Procedures – Every 4-Week Dosing**

	Screen	Treatment Period																			Follow-up Period			
Study Week	-4 to -1	1	1	5	9	13	17	21	25			26	27	29	33	37	41	45	49	53/ET	4*	10*	16*	
Study Day	-28 to -1	1	2 a	29	57	85	113	141	169	170 a	171 a	176 a	183 a	197	225	253	281	309	337	365	*Post Last Dose			
Visit Window +/- Days	0	-3 b	0	2	2	2	3	3	3	0	0	3	3	3	3	3	3	3	3	3	3	3	3	
Informed Consent	X																							
Outpatient Visit	X	X	X	X	X	X	X	X	X	X	X	X	X	X	X	X	X	X	X	X	X	X	X	
Inclusion/Exclusion Criteria	X	X																						
Medical History c	X																							
Vital Signs	X	X		X	X	X	X	X	X					X	X	X	X	X	X	X	X	X	X	
Physical Examination	X	X		X		X		X	X						X		X		X	X	X	X	X	
Body Weight and Height d	X								X								X						X	
12- lead ECG (triplicate)	X	X		X		X		X	X						X		X		X	X	X	X	X	
24-hour Urine for Creatinine Clearance and Protein	X																							
Extended Urinalysis e	X	EXTENDED URINALYSIS PERFORMED EVERY 14 DAYS e, f																			X	X	X	
Renal Biomarkers g	X	RENAL BIOMARKERS PERFORMED EVERY 14 DAYS f, g																			X h	X h	X h	
Serum Creatinine and Cys-C i, j		SERUM CREATININE and Cys-C PERFORMED EVERY 14 DAYS f, i																						
Genetic Testing		X																						
Chemistry Panel i, k	X	EVERY 14 DAYS f			X	X	X							X	X	X	X	X	X	X	X	X	X	X
Hematology i, k	X	HEMATOLOGY PERFORMED EVERY 14 DAYS f, k																			X h	X h	X h	
Platelet Function		X		X	X	X	X	X	X					X	X	X	X	X	X	X	X	X	X	X
Coagulation	X	X							X															
Hepatitis B, C, HIV	X																							
Thyroid Panel	X																							
hsCRP		X							X											X			X	
Plasma PK - ISIS 681257 l		X 	X 	X	X	X	X	X	X 	X 	X 	X	X	X		X				X	X	X	X	
ISIS 681257 Antibodies		X		X	X	X			X											X			X	

**Appendix A Schedule of Procedures – Every 4-Week Dosing *Continued***

	Screen	Treatment Period																			Follow-up Period			
Study Week	-4 to -1	1	1	5	9	13	17	21	25		26	27	29	33	37	41	45	49	53/ET	4*	10*	16*		
Study Day	-28 to -1	1	2 a	29	57	85	113	141	169	170 a	171 a	176 a	183 a	197	225	253	281	309	337	365	*Post Last Dose			
Visit Window +/- Days	0	-3 b	0	2	2	2	3	3	3	0	0	3	3	3	3	3	3	3	3	3	3	3	3	
FSH (women only, if applicable) i, m	X																							
Serum Pregnancy Test m	X	X		X	X	X	X	X	X					X	X	X	X	X	X	X	X	X	X	
Archived Serum & Plasma Samples j, n		X		X		X		X					X		X		X		X		X	X	X	
PD Panel l	X	X		X	X	X	X	X	X				X	X		X		X		X	X	X	X	
Lipid Panel l	X	X		X	X	X	X	X	X			X	X	X		X		X		X	X	X	X	
Lp(a) Characterization		X																						
Study Drug: SC Injection		EVERY 4-WEEK SUBCUTANEOUS ADMINISTRATION OF STUDY DRUG (Week 1 through Week 49/Day 337) o																						
Adverse Events	X	X	X	X	X	X	X	X	X	X	X			X	X	X	X	X	X	X	X	X	X	
Concomitant Medication	X	X	X	X	X	X	X	X	X	X	X			X	X	X	X	X	X	X	X	X	X	

All procedures and study samples are to be done pre-dose at respective visits, unless specified

- a Visit only required for patients in PK subgroup.
- b Day 1/Baseline assessments can be performed up to 3 days (-3 days) prior to the actual Day 1 visit, which is the day of first Study Drug dose.
- c Patient charts will be reviewed in order to collect disease associated medical history data such as CVD history.
- d Height only required at Screening.
- e All tests listed in Appendix B under Extended Urinalysis should be performed, including routine urinalysis, urine microscopy, UACR and UPCR.
- f Assessments and procedures to be conducted by either a home healthcare service or the Study Center. Patient Study Center visits must be no more than 4 weeks apart during the treatment period.
- g Urine samples for renal biomarkers will be collected. Sample analysis will be conducted in accordance with Safety Monitoring for Renal Function (Section 8.5.2).
- h During follow-up period, hematology sampling for platelet values and urine renal biomarker samples are taken every 14 days for 6 weeks after last dose of Study Drug, then every 6 weeks.
- i Serum Creatinine and Cys-C will be collected as a part of chemistry panel at visits when chemistry panel is performed, or as stand-alone samples at time points when a chemistry panel is not performed.
- j Blood samples to be collected after an overnight fast of at least 10 hours and preferably not more than 12 hours, unless tests are repeated for safety reasons.

## Appendix A Schedule of Procedures – Every 4-Week Dosing *Continued*

- k If the platelet value, serum creatinine or liver enzyme tests are uninterpretable (e.g., due to clumping, hemolysis or quantity not sufficient) a repeat blood specimen should be re-drawn as soon as possible (ideally within 7 days). All platelet count results will be reviewed promptly (within 48 hours of receipt) by the Investigator as per [Section 6.2.1](#). Any case of a platelet count  $\leq 50,000/\text{mm}^3$  should be reported in an expedited fashion to the Sponsor.
- l Refer to [Appendix C](#) for PK Sampling schedule.
- m Women who are not surgically sterile or post-menopausal.
- n Serum and plasma samples will be collected and stored for follow-up exploration of laboratory findings and/or AEs (e.g., measurement of cytokine and/or chemokine levels, measurement of additional markers of kidney function, measurement of antibodies, etc.) in this or subsequent clinical studies of ISIS 681257.
- o Patients will continue treatment in the study until the last patient enrolled reaches 6 months of exposure, and 50% of the enrolled patients have received Study Drug for 52 weeks. When both of these milestones are met, all patients will then enter a 16-week post-treatment follow-up period.

### Time (time is in reference to Study Drug administration):

- 1 24-hr from previous dose of Study Drug
- 2 48-hr from previous dose of Study Drug
- 3 Pre-dose, 1, 2, 4, 8, hrs post SC injection

## **Appendix B    List of Laboratory Analytes**

## Appendix B List of Laboratory Analytes

Based on emerging data from this or future studies, additional tests not listed below may be performed on stored samples to better characterize the profile of ISIS 681257 or other similar oligonucleotides.


Clinical Chemistry Panel
 
 
• Sodium
 
• Potassium
 
• Chloride
 
• Bicarbonate
 
• Total protein
 
• Albumin
 
• Calcium
 
• Magnesium
 
• Phosphorus
 
• Glucose
 
• BUN
 
• Creatinine
 
• Cholesterol
 
• Uric Acid
 
• Total bilirubin
 
• Direct (conjugated) bilirubin
 
• Indirect (unconjugated) bilirubin
 
• ALT
 
• AST
 
• ALP
 
• Creatinine kinase
 
• GGT
 
• Cys-C
 
	
Screening Tests
 
 
• Hepatitis B surface antigen
 
• Hepatitis C antibody
 
• HIV antibody
 
• FSH (women only)
 
• Serum <math>\beta</math>hCG (women only)
 
• TSH
 
• Free T4
 
• Free T3
 
 
Coagulation
 
 
• Fibrinogen
 
• Plasminogen
 
 
PD Panel
 
 
• Lp(a)
 
• OxPL-apoB
 
• OxPL-apo(a)
 
 
Lipid Panel
 
 
• Total Cholesterol
 
• LDL cholesterol
 
• HDL cholesterol
 
• ApoB
 
• Triglycerides
 
• VLDL
 
	
Lp(a) Characterization
 
 
• Apo(a) isoforms
 
 
Hematology
 
 
• Red blood cells
 
• Hemoglobin
 
• Hematocrit
 
• MCV, MCH, MCHC
 
• Platelets
 
• White blood cells (WBC)
 
• WBC Differential (% and absolute)                             
 
• Neutrophils
 
• Eosinophils
 
• Basophils
 
• Lymphocytes
 
• Monocytes
 
 
 
 
Pharmacokinetics
 
 
• ISIS 681257 (total full length ASO) levels in plasma
 
 
Immunogenicity
 
 
• Anti-ISIS 681257 antibodies
 
 
Genetic Testing
 
 
• LPA SNPs associated with elevated Lp(a)
 
	
Inflammatory
 
 
• hs-CRP
 
 
Extended Urinalysis
 
 
• Routine Urinalysis                             
 
- Color
 
- Appearance
 
- Specific gravity
 
- pH
 
- Protein
 
- Blood
 
- Glucose
 
- Ketones
 
- Bilirubin
 
- Urobilinogen
 
- Leukocyte esterase
 
- Nitrate
 
 
 
• Microscopic examination
 
• P/C Ratio (UPCR)
 
• A/C Ratio (UACR)
 
 
Renal Urine Biomarkers
 
 
• NGAL
 
• NAG
 
• KIM-1
 
• Cys-C
 
 
24 Hour Urine Test
 
 
• Creatinine clearance
 
• Protein
 
• Albumin
 

---	--	---	---

- 1 Plasma PK samples may also be used for profiling of drug binding proteins, bioanalytical method validation purposes, stability assessments, metabolite assessments, or to assess other actions of ISIS 681257 with plasma constituents
- 2 All samples will be collected, handled and stored under the conditions specified for the assays. Please refer to the study Laboratory Manual for details on the appropriate handling and storage methods for biomarker and other samples.
- 3 To be performed during Screening upon confirmation of eligibility

## **Appendix C    PK Sampling Schedule**

Sampling Schedule for Weekly and Every 2-Week Dosing Cohorts

Sampling Schedule for Every 4-Week Dosing Cohorts

### Appendix C PK Sampling Schedule

Blood samples for the determination of plasma ISIS 681257 concentrations will be collected prior to dosing, and at various times throughout the dosing and post-treatment follow-up period as noted in the tables below. Plasma PK samples may also be used for profiling of drug binding proteins, bioanalytical method validation purposes, stability and metabolite assessments, immunogenicity testing (or possibly for purposes of immunogenicity assay development and/or validation), or to assess other actions of ISIS 681257 with plasma constituents. Extensive PK samples will be collected in PK subgroup only (10 subjects per cohort) (see tables below):

#### Sampling Schedule for Weekly and Every 2-Week Dosing Cohorts

Study Week	Treatment Period													Follow-up Period			
	1	1	5	9	13	17	21	25	27			29	37	53	4*	10*	16*
Study Day	1	2	29	57	85	113	141	169	183	184	185	197	253	365	*Post Last Dose		
All Patients	Pre-dose	NA	Pre-dose	Pre-dose	Pre-dose	Pre-dose	Pre-dose	Pre-dose	Pre-dose	NA	NA	NA	Pre-dose	Pre-dose	Anytime	Anytime	Anytime
PK Subgroup Only	Pre-dose, 1, 2, 4, & 8-hr 	24-hr 	Pre-dose	Pre-dose	Pre-dose	Pre-dose	Pre-dose	Pre-dose	Pre-dose, 1, 2, 4, & 8-hr 	24-hr 	48-hr 	Pre-dose	Pre-dose	Pre-dose	Anytime	Anytime	Anytime

- 1 Window of (-) 2 hrs
- 2 24-hr from previous dose of Study Drug. Window of (+/-) 4 hours
- 3 48-hr from previous dose of Study Drug. Window of (+/-) 6 hours

**Appendix C PK Sampling Schedule *Continued***

**Sampling Schedule for Every 4-Week Dosing Cohorts**

	Treatment Period															Follow-up Period		
Study Week	1	1	5	9	13	17	21	25			26	27	29	37	53	4*	10*	16*
Study Day	1	2	29	57	85	113	141	169	170	171	176	183	197	253	365	*Post Last Dose		
All Patients	Pre-dose	NA	Pre-dose	Pre-dose	Pre-dose	Pre-dose	Pre-dose	Pre-dose,	NA	NA	NA	NA	NA	Pre-dose	Pre-dose	Anytime	Anytime	Anytime
PK Sub-group only	Pre-dose, 1, 2, 4, and 8-hr 	24-hr 	Pre-dose	Pre-dose	Pre-dose	Pre-dose	Pre-dose	Pre-dose, 1, 2, 4, and 8-hr 	24-hr 	48-hr 	Anytime	Anytime	Pre-dose	Pre-dose	Pre-dose	Anytime	Anytime	Anytime

- 1 Window of (-) 2 hours allowed
- 2 24-hr from previous dose of Study Drug. Window of (+/-) 4 hours allowed
- 3 48-hr from previous dose of Study Drug. Window of (+/-) 6 hours allowed

## **Appendix D      Grading Scale for Adverse Events Relating to Laboratory Abnormalities**

## Appendix D Grading Scale for Adverse Events Relating to Laboratory Abnormalities

The following grading recommendations for adverse events relating to lab test abnormalities are based upon the Common Terminology Criteria for Adverse Events (CTCAE) Version 4.03, June 2010.

Adverse Event	Mild	Moderate	Severe
Hematology			
aPTT prolonged	>ULN - 1.5 x ULN	>1.5 - 2.5 x ULN	>2.5 x ULN; hemorrhage
Eosinophils increased f	650 – 1,500 cell/mm 	1,501 - 5,000 cell/mm 	>5,000 cell/mm 
Fibrinogen decreased	<1.0 - 0.75 x LLN or <25% decrease from baseline	<0.75 - 0.5 x LLN or 25 - <50% decrease from baseline	<0.5 x LLN or ≥50% decrease from baseline
Hemoglobin decreased (Anemia)	Hemoglobin (Hgb) <LLN - 10.0 g/dL; <LLN - 6.2 mmol/L; <LLN - 100 g/L	Hgb <10.0 - 8.0 g/dL; <6.2 - 4.9 mmol/L; <100 - 80g/L	Hgb <8.0 g/dL; <4.9 mmol/L; <80 g/L; transfusion indicated
Hemoglobin increased	Increase in >0 - 2 g/dL above ULN or above baseline if baseline is above ULN	Increase in >2 - 4 g/dL above ULN or above baseline if baseline is above ULN	Increase in >4 g/dL above ULN or above baseline if baseline is above ULN
INR increased	>1 - 1.5 x ULN; >1 - 1.5 times above baseline if on anticoagulation	>1.5 - 2.5 x ULN; >1.5 - 2.5 times above baseline if on anticoagulation	>2.5 x ULN; >2.5 times above baseline if on anticoagulation
Lymphocyte count decreased	<LLN - 800/mm  ; <LLN - 0.8 x 10  /L	<800 - 500/mm  ; <0.8 - 0.5 x 10  /L	<500 /mm  ; <0.5 x 10  /L
Lymphocyte count increased	-	>4000/mm  - 20,000/mm 	>20,000/mm 
Neutrophil count decreased	<LLN - 1500/mm  ; <LLN - 1.5 x 10  /L	<1500 - 1000/mm  ; <1.5 - 1.0 x 10  /L	<1000/mm  ; <1.0 x 10  /L
Platelet count decreased	<LLN - 75,000/mm  ; <LLN - 75.0 x 10  /L	<75,000 - 50,000/mm  ; <75.0 - 50.0 x 10  /L	<50,000/mm  ; <50.0 x 10  /L
White blood cell decreased	<LLN - 3000/mm  ; <LLN - 3.0 x 10  /L	<3000 - 2000/mm  ; <3.0 - 2.0 x 10  /L	<2000/mm  ; <2.0 x 10  /L
Chemistry			
Acidosis	pH <normal, but ≥7.3	-	pH <7.3
Alanine aminotransferase increased	>ULN - 3.0 x ULN	>3.0 - 5.0 x ULN	>5.0 x ULN
Alkaline phosphatase increased	>ULN - 2.5 x ULN	>2.5 - 5.0 x ULN	>5.0 x ULN
Alkalosis	pH >normal, but ≤7.5	-	pH >7.5
Aspartate aminotransferase increased	>ULN - 3.0 x ULN	>3.0 - 5.0 x ULN	>5.0 x ULN
Blood bilirubin increased	>ULN - 1.5 x ULN	>1.5 - 3.0 x ULN	>3.0 x ULN
Cardiac troponin I increased	Levels above the upper limit of normal and below the level of myocardial infarction as defined by the manufacturer	-	Levels consistent with myocardial infarction as defined by the manufacturer

**Appendix D Grading Scale for Adverse Events Relating to Laboratory Abnormalities**  
*Continued*

Adverse Event	Mild	Moderate	Severe
Cardiac troponin T increased	Levels above the upper limit of normal and below the level of myocardial infarction as defined by the manufacturer	-	Levels consistent with myocardial infarction as defined by the manufacturer
CD4 lymphocytes decreased	<LLN - 500/mm  ; <LLN - 0.5 x 10  /L	<500 - 200/mm  ; <0.5 - 0.2 x 10  /L	<200/mm  ; <0.2 x 10  /L
CPK increased*	>ULN - <6 ULN	6 - 10 x ULN	>10 x ULN
Creatinine increased	>1 - 1.5 x baseline; >ULN - 1.5 x ULN	>1.5 - 3.0 x baseline; >1.5 - 3.0 x ULN	>3.0 x baseline; >3.0 x ULN
GGT increased	>ULN - 2.5 x ULN	>2.5 - 5.0 x ULN	>5.0 x ULN
Hypercalcemia	Corrected serum calcium of >ULN - 11.5 mg/dL; >ULN - 2.9 mmol/L; Ionized calcium >ULN - 1.5 mmol/L	Corrected serum calcium of >11.5 - 12.5 mg/dL; >2.9 - 3.1 mmol/L; Ionized calcium >1.5 - 1.6 mmol/L; symptomatic	Corrected serum calcium of >12.5 mg/dL; >3.1 mmol/L; Ionized calcium >1.6 mmol/L; hospitalization indicated
Hyperglycemia	Fasting glucose value >ULN - 160 mg/dL; Fasting glucose value >ULN - 8.9 mmol/L	Fasting glucose value >160 - 250 mg/dL; Fasting glucose value >8.9 - 13.9 mmol/L	>250 mg/dL; >13.9 mmol/L; hospitalization indicated
Hyperkalemia	>ULN - 5.5 mmol/L	>5.5 - 6.0 mmol/L	>6.0; hospitalization indicated
Hypermagnesemia	>ULN - 3.0 mg/dL; >ULN - 1.23 mmol/L	-	>3.0 mg/dL; >1.23 mmol/L
Hypernatremia	>ULN - 150 mmol/L	>150 - 155 mmol/L	>155 mmol/L; hospitalization indicated
Hyperuricemia	>ULN - 10 mg/dL (0.59 mmol/L) without physiologic consequences	-	>ULN - 10 mg/dL (0.59 mmol/L) with physiologic consequences
Hypoalbuminemia	<LLN - 3 g/dL; <LLN - 30 g/L	<3 - 2 g/dL; <30 - 20 g/L	<2 g/dL; <20 g/L
Hypocalcemia	Corrected serum calcium of <LLN - 8.0 mg/dL; <LLN - 2.0 mmol/L; Ionized calcium <LLN - 1.0 mmol/L	Corrected serum calcium of <8.0 - 7.0 mg/dL; <2.0 - 1.75 mmol/L; Ionized calcium <1.0 - 0.9 mmol/L; symptomatic	Corrected serum calcium of <7.0 mg/dL; <1.75 mmol/L; Ionized calcium <0.9 mmol/L; hospitalization indicated
Hypoglycemia	<LLN - 55 mg/dL; <LLN - 3.0 mmol/L	<55 mg/dL; <3.0 mmol/L	<40 mg/dL (<2.2 mmol/L) AND requires assistance of another person to actively administer carbohydrates, glucagon, or take other corrective actions †
Hypokalemia	<LLN - 3.0 mmol/L	<LLN - 3.0 mmol/L; symptomatic; intervention indicated	<3.0 mmol/L; hospitalization indicated
Hypomagnesemia	<LLN - 1.2 mg/dL; <LLN - 0.5 mmol/L	<1.2 - 0.9 mg/dL; <0.5 - 0.4 mmol/L	<0.9 mg/dL; <0.4 mmol/L
Hyponatremia	<LLN - 130 mmol/L	-	<130 mmol/L
Hypophosphatemia	<LLN - 2.5 mg/dL; <LLN - 0.8 mmol/L	<2.5 - 2.0 mg/dL; <0.8 - 0.6 mmol/L	<2.0 mg/dL; <0.6 mmol/L
Lipase increased	>ULN - 1.5 x ULN	>1.5 - 2.0 x ULN	>2.0 x ULN
Serum amylase increased	>ULN - 1.5 x ULN	>1.5 - 2.0 x ULN	>2.0 x ULN

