#### **9.4.3.2 Severity**

The severity of AEs and SAEs will be graded based on criteria from the Common Terminology Criteria for Adverse Events (CTCAE) Version 4.03, June 2010 (refer to [Appendix D](#)). Any AE not listed in Appendix D will be graded as follows:

- **Mild:** The event is easily tolerated by the subject and does not affect the subject's usual daily activities
- **Moderate:** The event causes the subject more discomfort and interrupts the subject's usual daily activities
- **Severe:** The event is incapacitating and causes considerable interference with the subject's usual daily activities

If the event is an SAE, then all applicable seriousness criteria must be indicated (criteria listed in [Section 9.3.3](#)).

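### Both hyperuricemia cells in Appendix D stop at 10 mg/dL, so the table read alone gives no severity grade to a higher uric acid

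*Protocol*

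**What the plan says.** Section 9.4.3.2 sets the grading rule: "The severity of AEs and SAEs will be graded based on criteria from the Common Terminology Criteria for Adverse Events (CTCAE) Version 4.03, June 2010", with a pointer to Appendix D. It then gives general Mild, Moderate and Severe definitions with a limited scope: "Any AE not listed in Appendix D will be graded as follows".

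The hyperuricemia row of Appendix D reads:

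- Mild: ">ULN - 10 mg/dL (0.59 mmol/L) without physiologic consequences"
- Moderate: no entry
- Severe: ">ULN - 10 mg/dL (0.59 mmol/L) with physiologic consequences"

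Appendix D describes its entries as recommendations based on CTCAE 4.03. Appendix B lists uric acid in the clinical chemistry panel, which Appendix A schedules at screening, during treatment and in follow-up.

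**The concern.** A severity scale should give a grade to every abnormal value, and above all to the most abnormal ones. This row covers values from the upper limit of normal (ULN) to 10 mg/dL and nothing beyond. The generic definitions that might have caught the remainder are switched off for listed events, and hyperuricemia is listed.

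At stake is the severity field on the adverse event form, which Section 9.4.3 asks the investigator to complete. For a hyperuricemia event above 10 mg/dL, an investigator working from the table has to improvise. The analysis plan cannot repair this later, because the grade is assigned at the site from this table.

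**Working it through.** The protocol states no figure to reproduce here. The check applies the printed cells literally and then compares the row with the rest of the table.

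**Inputs.** The Mild and Severe cells of the hyperuricemia row (Appendix D) and the scope of the generic definitions (Section 9.4.3.2). The protocol does not give the ULN for uric acid, so 6, 7 and 8 mg/dL are assumed.

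**Rule as printed.** If ULN < value ≤ 10 mg/dL, the grade is Mild without physiologic consequences and Severe with them. Otherwise the row gives no grade.

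| Uric acid (mg/dL) | Without consequences | With consequences |
|---|---|---|
| 8.5 | Mild | Severe |
| 10 | Mild | Severe |
| 10.1 | none | none |
| 12 | none | none |
| 15 | none | none |

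The result is the same for all three assumed ULNs, because the gap starts at 10 mg/dL and does not depend on the ULN.

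**Is the limit a unit slip?** Assuming a molar mass of 168.11 g/mol, 10 mg/dL = 100 mg/L, and 100 / 168.11 = 0.595 mmol/L. The printed 0.59 mmol/L agrees, so the two units describe the same limit.

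**Is a closed top band the table's convention?** No. Four other numeric rows also have a blank Moderate cell and a single cut-off, and in each the Severe cell runs on beyond the Mild limit:

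- Hypermagnesemia: Mild ends at 3.0 mg/dL, Severe is ">3.0 mg/dL; >1.23 mmol/L"
- Hyponatremia: Mild ends at 130 mmol/L, Severe is below 130 mmol/L
- Acidosis: Mild ends at pH 7.3, Severe is below 7.3
- Alkalosis: Mild ends at pH 7.5, Severe is above 7.5

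Hypokalemia also repeats one numeric range in two cells separated by symptoms, but its Severe cell is open below 3.0 mmol/L. Among the numeric rows, hyperuricemia alone is closed at the abnormal end.

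**Is it a text-extraction fault?** Unlikely. The file contains three printings of Appendix D, and the row is identical in all of them.

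**Does another rule supply the grade?** The generic definitions in Section 9.4.3.2 do not, since hyperuricemia is a listed event.

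**The case against.** Three stronger readings are tempting, and the documents support none of them.

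*That such an event cannot be graded at all.* Section 9.4.3.2 names CTCAE 4.03 as the standard and Appendix D calls its own entries recommendations. A grader could go back to that standard when the row fails. What it gives above 10 mg/dL is not in these documents, so the defensible statement is narrower: the table read alone gives no grade. Sites might resolve the gap differently, but nothing in the protocol shows that they would.

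*That the gap weakens renal safety or the choice of dose.* Dose selection in Section 10.1.4 does weigh renal injury, but uric acid is not named as a marker of it. The renal alerts in Section 8.5.2 use creatinine clearance, the albumin and protein to creatinine ratios, and serum creatinine. The stopping rules in Section 8.6.2 use CKD-EPI, 24-hour urine protein and creatinine clearance. The renal urine biomarkers in Appendix B are NGAL, NAG, KIM-1 and Cys-C. The safety endpoints in Section 10.1.3 do not single out uric acid.

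*That every value above 10 mg/dL should simply become Severe.* The printed row separates its grades only by physiologic consequences. Extending Severe to all higher values would make 10.1 mg/dL without consequences Severe, and the documents do not settle that.

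It is also fair to say that few records are exposed. Under Section 9.5.1 a laboratory abnormality judged not clinically significant is not reported as an adverse event, and an underlying diagnosis is preferred to a laboratory term. The laboratory summaries in Section 10.6.2.2 need no adverse event grade. All of this limits the importance of the point, but none of it puts a grade in the table above 10 mg/dL.

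**Conclusion.** The point holds as a minor error in the grading table. Both filled cells of the hyperuricemia row end at 10 mg/dL, so the row ranks 9 mg/dL with physiologic consequences as Severe and is silent on 12 mg/dL with the same consequences. The restriction on the generic definitions leaves that silence in place. The contrast with every other numeric row suggests a transcription slip and not a deliberate choice.

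The consequence is confined to the severity grade of hyperuricemia adverse events above 10 mg/dL, in any arm. Their number cannot be derived from the documents and is probably low. No stopping rule, alert, listed endpoint or dose-selection criterion uses this grade. The conclusion rests on reading the cells literally and does not depend on the assumed ULN.

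**What to change.** Correct the hyperuricemia row against its stated source, CTCAE 4.03, so that every value above 10 mg/dL (0.59 mmol/L) has a grade. Values above 10 mg/dL with physiologic consequences should rank no lower than Severe, since the row already ranks lower values with consequences as Severe. For values above 10 mg/dL without consequences, the sponsor should state the intended grade explicitly.

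The cost is an edit to one table row. No dose, schedule, stopping rule or analysis changes.
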